Low-Intensity Focused Ultrasound Pulsation for Treatment of Motor Deficits in Parkinson's Disease

NCT04593875

October 16, 2022

APPROACH

Participants. Participants will consist of 30 adults, aged 18 to 85 years, diagnosed with Parkinson's Disease (PD).

Subject Recruitment. Subjects will be recruited using flyers and brochures distributed physically and online, as well as from the UCLA Movement Disorder Program in collaboration with [name], MD, PhD. A subpage on the Staglin IMHRO Center for Cognitive Neuroscience (henceforth CCN) website will include study information and an interest form to submit contact information if interested. Recruitment mailers will be distributed to doctor's offices and clinics, where patients (or their doctor's office, upon patient's request) can mail us their contact information if interested in the study.

Screening. Participants will be contacted by study staff who will conduct a telephone screening to ensure eligibility and suitability for MRI.

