fMRI Validated LIFUP stimulation. We will use a Brainsonix ultrasound system with a transducer that fits in the 20-channel head coil. Participants will have the low-intensity focused ultrasound pulsation (LIFUP) transducer approximately aimed at the internal globus pallidus (GPI) using skin surface fiducials and gently strapped in place to their head. To minimize the ultrasound energy's exposure to air, a gel pad will be placed between the transducer and the participant's scalp. Participants will then be placed into the scanner where head scout scans will be used to guide more precise targeting adjustments. Once targeting is complete, a T1 image will verify the position of the LIFUP transducer and allow for estimation of the spatial location of the sonication beam focus (approximately 5mm long x 7mm diameter). Participants will receive active sonication at one visit and sham sonication at the other, the order of which will be randomized and counterbalanced across participants. The sonication protocol will consist of 20 ultrasound sonifications in a 30 s ON, 30 s OFF fashion at 650KHz, $Ispta \leq 720 \text{ mW/cm}^2$, 5% duty cycle, 0.5ms pulse width, 73.15mvP-P amplitude, and 100Hz pulse repetition frequency. For sham sonication, the gel pad will block close to all of the ultrasound energy from the transducer. For active sonication, the gel pad will allow the ultrasound energy to pass through. These gel pads are identical in appearance. Resting state fMRI (rs-fMRI) will be collected simultaneously with LIFUP (or sham) sonication.

MRI Data Acquisition: We will use a 3-Tesla Siemens PRISMA scanner. We will collect high-resolution 0.8 mm^3 T1-weighted images, pseudo-continuous arterial spin labeling (PCASL) images, and rs-fMRI images. Total time in the scanner will be approximately 75 minutes each session.

Analysis and Publications. MRI data analysis will begin immediately during data collection, as structural and functional MRI are used to ensure successful targeting of LIFUP sonication. Group level analysis will occur after data from 30 subjects have been collected.

This project has four main aims:

#1: Validate basal ganglia-thalamocortical (BGTC) network perfusion and resting state functional connectivity (rs-FC) is associated with Parkinson's Disease (PD) deficits in cognition and motor impairments.

#2: Use LIFUP to modulate neural activity in the GPI, and PCASL pre- and post- LIFUP to assess up-regulation of BGTC network perfusion.

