Perfusion. PCASL is an arterial spin labeling technique that measures cerebral blood flow. It produces a perfusion image with voxel values representing local perfusion rates. Within FSL we will perform a voxel-wise repeated measures analysis between the pre-LIFUP and post-LIFUP PCASL scans. By examining the differences between these two scans, we can determine the effects that LIFUP has on perfusion in the target region and other connected regions. We will also perform a repeated measures analysis of perfusion between conditions (LIFUP vs. sham). By examining subjects receiving sham on visit 2, we can compare pre-sham resting state fMRI and PCASL to the pre-LIFUP values at visit one, to determine the persistence of blood flow effects over a 2-week interval. This will suggest how frequently LIFUP would need to be administered during a more comprehensive clinical trial.

Motor Assessment. Subjects will undergo a motor evaluation with assessments of motor symptoms such as a grooved pegboard task, a 15-second recording of forearm and hand tremor, and dynamometer grip strength measurements. They will also complete The Essential Tremor Rating Assessment Scale (TETRAS) and the Unified Parkinson's Disease Rating Scale (UPDRS). The motor testing portion of the UPDRS will be video-recorded for research staff to review after the session in order to maximize rating accuracy. Any recordings containing participants faces will be exclusively stored locally on UCLA-owned devices kept in a locked room; any video transferred off these devices will first be edited to remove faces and any other identifying information. The original footage will be deleted once this editing is complete. Participants will complete all of these assessments both before and after the MRI/LIFUP portion of each session. We will also ask the participant's partner or caregiver to complete part 1 of the TETRAS during the first virtual session. In addition to the measurements taken during the in-person and virtual sessions, we will ask participants to wear a watch-style device called the Personal KinetiGraph (PKG) starting one week prior to their first in-person session and ending one week after their second in-person session. This device provides round-the-clock monitoring of tremor activity and sleep quality. Additionally, immediately after administering LIFUP or sham stimulation, we will be asking participants open-ended questions about any perceived changes.

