- During in-person session #2 (two weeks after in-person session #1), we will administer pre-LIFUP behavioral and motor testing, MRI, either LIFUP or sham stimulation (whichever was not received during the first session), and post-LIFUP motor testing.
- 48-72 hours after each in-person session, behavioral testing will be administered, as well as motor testing that can be conducted remotely.
- 4 and 7 days after each in-person session, a brief follow-up call will be conducted.
- Participants will be wearing the PKG device round-the-clock from one week prior to the first in-person session until one week after the second in-person session.
- The independent variable is the type of LIFUP modulation we will perform: active stimulation vs. sham stimulation.
- The dependent variables are: resting-state functional connectivity, perfusion, severity of motor symptoms, severity of psychological symptoms, and performance on the probabilistic learning task.

Detailed Design

Pre-screen: when we are put in contact with a potential participant, we will ask them to undergo a brief screening over the phone. The purpose of this session is exclusively to determine eligibility with respect to the following inclusion and exclusion criteria:

- **Inclusion Criteria:** (i) diagnosis of PD, (ii) age 18-85, (iii) fluent in English, (iv) hearing and vision normal or corrected-to-normal, and (v) willing and able to provide informed consent
- **Exclusion Criteria:** (i) mobility issues requiring use of a wheelchair or walker, (ii) significant cognitive impairment, (iii) history of neurological disorder other than Parkinson's, (iv) history of psychiatric disorders other than sleep disorders, anxiety disorders, and major depressive disorder, (v) pre-PD history of sleep disorders, anxiety disorders, and/or major depressive disorder, (vi) contraindication to MRI, (vii) medication changes within past 6 weeks or planned changes in next 6 weeks, (viii) pregnant or planning to become pregnant, (ix) history of medical event(s) likely to result in neurological abnormalities, (x) uncontrolled diabetes or hypertension, (xi) diagnosis of severe lung, liver, heart, or kidney disease, (xii) history of alcohol or substance abuse (other than nicotine or caffeine)

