The only data that will be retained about this screen is whether the participant is currently eligible, ineligible, or eligible at some future date, as well as their necessary contact information and any information necessary to verify MRI safety. No other record will be kept of the contents of the potential participant's answers.

Remote Session 1 [90 minutes]

The aim of this session is to (a) complete informed consent procedures, (b) evaluate cognitive status via the TICS-M (c) complete MRI safety screening procedures, (d) obtain participant demographic and medication information, (e) have caretaker complete part 1 of the TETRAS, and (f) schedule all other sessions

Remote PKG Setup Session [approx. 10 minutes]

The aim of this session is to (a) obtain a recording of the participant putting on the PKG device to ensure correct setup and (b) familiarize the participant with the usage of the device. Participant faces and voices will be removed from recordings before they are transferred from UCLA-owned devices to the UCLAHealth Box server. The PKG device will be worn from one week prior to the first in-person session to one week after the second in-person session. To collect continuous tremor data, the PKG device is to be worn round-the-clock, except for when participant is swimming, showering, syncing the device weekly, or in a LIFUP/MRI session.

In-Person Session 1 [approx. 4.5 hours]

This session will take place one week after the PKG setup session. The aim of this session is to (a) complete pre-LIFUP motor assessments (UPDRS, TETRAS, 1-minute forearm recording, grip strength and grooved pegboard tasks), (b) complete pre-LIFUP psychological assessments (SSS, STAI, RBDSQ, QUIP-RS, BDI), (c) perform neuronavigation-guided LIFUP or sham stimulation during rsfMRI, (d) collect information on any perceived changes immediately post-LIFUP, (e) collect pre-LIFUP high res T1w, PCASL, and rsfMRI scans and post-LIFUP PCASL and rsfMRI scans, (f) complete post-LIFUP motor assessments (UPDRS part 3, TETRAS part 2, grip strength and grooved pegboard tasks), and (g) complete post-LIFUP psychological assessments (SSS, PCQ).

Post-LIFUP Remote Session 1 [60 minutes]

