This session will take place 48-72 hours after the first in-person session. The aim of this session is to (a) complete post-LIFUP motor assessments that can be administered remotely (UPDRS parts 1, 2, and 4, TETRAS part 1), (b) complete post-LIFUP psychological assessments (SSS, BDI, RBDSQ, STAI-State, probabilistic learning task), and (c) collect information on any perceived changes not covered in the motor and psychological assessments.

In-Person Session 2 [approx. 4 hours]

This session will take place two weeks after the first in-person session. The aim of this session is to (a) complete pre-LIFUP motor assessments (UPDRS, TETRAS, 1-minute forearm recording, grip strength and grooved pegboard tasks), (b) complete pre-LIFUP psychological assessments (SSS, STAI-State, RBDSQ, BDI), (c) perform neuronavigation-guided LIFUP or sham stimulation during rsfMRI, (d) collect information on any perceived changes immediately post-LIFUP, (e) collect pre-LIFUP PCASL and rsfMRI scans and post-LIFUP PCASL and rsfMRI scans, (f) complete post-LIFUP motor assessments (UPDRS part 3, TETRAS part 2, grip strength and grooved pegboard tasks), and (g) complete post-LIFUP psychological assessments (SSS, PCQ).

Post-LIFUP Remote Session 2 [60 minutes]

This session will take place 48-72 hours after the first in-person session. The aim of this session is to (a) complete post-LIFUP motor assessments that can be administered remotely (UPDRS parts 1, 2, and 4, TETRAS part 1), (b) complete post-LIFUP psychological assessments (SSS,

BDI, RBDSQ, STAI-State, probabilistic learning task), and (c) collect information on any perceived changes not covered in the motor and psychological assessments.

Four-day Post-LIFUP Follow-Up Calls [approx. 5 min each]

These calls will take place four days after each in-person session. The aim of these calls is to collect information on any perceived changes since the LIFUP session or the post-LIFUP Zoom session.

One-week Post-LIFUP Follow-Up Call 1 [approx. 10 min]

This call will take place seven days after the first in-person session. The aim of these calls is to (a) collect information on any perceived changes since the LIFUP session or prior follow-up sessions, and (b) walk the participant through the process of syncing the PKG device in order to ensure successful data transfer.

One-week Post-LIFUP Follow-Up Call 2 [approx. 10 min]

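### The two-week persistence comparison has no concurrent control, so a lasting LIFUP effect cannot be told apart from a visit-1-to-visit-2 change, although sham-first participants have the same two scans

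*Combined protocol and SAP*

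**What the plan says.** The Perfusion paragraph (under PROCEDURES) sets up the persistence question with "By examining subjects receiving sham on visit 2". Because visit 2 gives whichever condition was not given at visit 1 (Design Overview), these are the LIFUP-first participants. In them the plan will "compare pre-sham resting state fMRI and PCASL to the pre-LIFUP values at visit one, to determine the persistence of blood flow effects" over two weeks. No concurrent group, visit term or sequence term is named for this contrast. The stated use is: "This will suggest how frequently LIFUP would need to be administered during a more comprehensive clinical trial".

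Other parts of the document bear on the point:

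- **Sample size** (Participants): "Participants will consist of 30 adults, aged 18 to 85 years".
- **Order of conditions** (fMRI Validated LIFUP stimulation): "the order of which will be randomized and counterbalanced across participants". The split between the two orders is not stated; 15 and 15 is the natural reading.
- **Scans at visit 1** (In-Person Session 1): "collect pre-LIFUP high res T1w, PCASL, and rsfMRI scans and post-LIFUP PCASL and rsfMRI scans".
- **Scans at visit 2** (In-Person Session 2): "collect pre-LIFUP PCASL and rsfMRI scans and post-LIFUP PCASL and rsfMRI scans".

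Both session descriptions cover LIFUP and sham alike, so the pre-stimulation scans are taken in every participant at both visits. The same Perfusion paragraph also plans a repeated measures comparison of LIFUP with sham, but it is not tied to the two-week question.

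**The concern.** The planned contrast is a before-after difference in a group that was all treated in between. Using each participant's own visit-1 scan removes stable differences between people. It does not remove anything that shifts systematically between a first and a second scanning visit, such as familiarity with the scanner or lower anxiety. Such a shift could pass for a lasting LIFUP effect or cancel a real one.

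The result has a declared use, informing how often LIFUP is given in a later trial. It is also the only stated imaging comparison that bears on whether the first session carries over into the second. A randomised comparison group with the same two scans is already in the design but is not used for this question.

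**Working it through.** **No figure to reproduce.** The documents give no alpha, power, effect size or SD for this contrast. The first step is about identifiability and needs no numbers; the rest is illustration.

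**1. What each contrast estimates.** Let c be the effect of active LIFUP still present at two weeks, and v the systematic visit-1-to-visit-2 change in pre-stimulation scans, taken as common to both orders.

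| Group | Given between the two pre-stimulation scans | Expected change |
|---|---|---|
| LIFUP-first | active LIFUP | c + v |
| Sham-first | sham | v |

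The plan uses the first row alone, so it estimates c + v. The difference between rows is (c + v) − v = c. Randomised order supports a common v. Strictly, c is then the lasting effect beyond sham, because the sham pad is said to block nearly all, not all, of the energy.

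**2. Assumptions for the illustration.** 15 participants per order (30/2), no dropout, one summary region, no multiplicity correction, two-sided 5% test, and all effects in units of the SD of the visit-to-visit change.

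**3. False positives when c = 0.** One-sample t test, n = 15, 14 df, noncentrality v·√15:

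| v (SD) | P(significant), planned contrast |
|---|---|
| 0 | 5.0% |
| 0.1 | 6.5% |
| 0.2 | 11.2% |
| 0.3 | 19.2% |
| 0.5 | 43.8% |

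At an illustrative per-voxel threshold of 0.001, shifts of 0.3 and 0.5 SD give 1.0% and 4.5% instead of 0.1%. With the sham-first control a common shift cancels. In 100,000 simulated trials at each of several shifts from 0 to 0.8 SD, the two-sample test rejected in 4.9% to 5.1%.

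**4. Masking.** The planned contrast has 80% power at c = 0.778 SD when v = 0. With an opposite shift the net effect is 0.778 minus the shift:

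| Opposite shift (SD) | Net effect (SD) | Power |
|---|---|---|
| 0.2 | 0.578 | 55% |
| 0.3 | 0.478 | 41% |
| 0.5 | 0.278 | 17% |

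With no shift, power falls below 50% only for effects under about 0.54 SD.

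**5. Price of the control.**

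| | Planned (n = 15) | Controlled (15 vs 15) |
|---|---|---|
| Standard error (SD units) | √(1/15) = 0.258 | √(2/15) = 0.365 |
| 95% CI half-width | 2.145 × 0.258 = 0.55 | 2.048 × 0.365 = 0.75 |
| Effect with 80% power | 0.78 | 1.06 |
| Power at c = 0.778, v = 0 | 80% | 54% |

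Adjusting for the visit-1 value multiplies the residual SD by √((1 + r)/2), where r is the test-retest correlation. For assumed r = 0.3, 0.5, 0.7 and 0.9, 80% power then needs 0.86, 0.92, 0.98 and 1.03 SD. Power at 0.778 SD runs from about 72% (r = 0.3) to 56% (r = 0.9).

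**The case against.** The strongest objection is that the size of the problem is entirely assumed. Nothing in the documents supports a visit shift of 0.3 or 0.5 SD; at 0.1 SD the false-positive rate rises only from 5% to 6.5%. The control also has a price. On mean squared error the unadjusted controlled estimate is better only if v exceeds √(2/15 − 1/15) = 0.26 SD, or about 0.14 to 0.24 SD with baseline adjustment at r = 0.3 to 0.9. For smaller shifts the planned contrast is on average the closer estimate.

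That stands as a caution about magnitude and as a reason to show the within-group change as well. It does not rescue the planned contrast as evidence of persistence: its narrower interval is centred on c + v, and no data within it reveal how large v is.

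Other points for the plan:

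- **Mitigation.** The exclusion criteria rule out "medication changes within past 6 weeks or planned changes in next 6 weeks", and state anxiety and sleepiness are recorded before both scans. This helps, but no adjustment of this contrast is stated, and covariates do not replace a control.
- **Drift.** Scanner drift would act as a visit effect only if it ran mainly one way across participants scanned on different dates (staggered enrolment is assumed). It is a weaker example than familiarity or anxiety.
- **Status.** Persistence is not one of the four aims and the wording is tentative. This limits the consequence, but the declared use for a later trial remains.
- **The LIFUP-versus-sham analysis.** It compares conditions, and no visit or sequence term is given, so it does not supply the missing control.

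**Conclusion.** The concern holds. As planned, a two-week change in the LIFUP-first group cannot be attributed to LIFUP, and the absence of a change cannot be read as absence of persistence. The confounding follows from the design of the contrast and is certain. Its practical size is unknown, because the error rates above depend on an assumed visit shift, an even split, full follow-up and a single region. Voxel-wise testing and exclusions for head motion would alter the power figures but not the conclusion.

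The damage is limited to the persistence claim and to any frequency or carryover inference drawn from it. The separate LIFUP-versus-sham comparison is not put in doubt by this point. The change should be made; it is not fatal to the study.

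**What to change.** Replace the persistence sentence in the Perfusion paragraph with:

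> Persistence will be estimated as the visit-1-to-visit-2 change in pre-stimulation PCASL perfusion and rs-FC in LIFUP-first participants minus the same change in sham-first participants, adjusted for the visit-1 pre-stimulation value, and reported with a 95% CI. A non-significant result will not be taken as evidence of no persistence.

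Two additions would complete it. Name in advance the perfusion region and the network summary to which the estimate applies, since the planned analyses are voxel-wise and ICA-based. Report the within-group changes alongside, as description only.

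The cost is analysis wording and the choice of those summaries; no scan or participant is added. The price is the loss of precision shown above, so any statement about treatment frequency has to be more cautious.

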Psychological Assessment. After giving informed consent, subjects will be evaluated for cognitive status with the Modified Telephone Interview for Cognitive Status (TICS-M). Subjects will undergo a baseline psychological evaluation at their first in-person visit composed of the State Trait Anxiety Inventory (STAI), Beck's Depression Inventory (BDI), the Questionnaire for Impulsive-Compulsive Disorders in Parkinson's Disease–Rating Scale (QUIP-RS), and the REM Sleep Behavior Disorder Screening Questionnaire (RBDSQ). The BDI, the RBDSQ, the "state" portion of the STAI, and an open-ended question about any perceived changes not covered by the inventories will also be completed before MRI/LIFUP at the second in-person session and at both follow-up Zoom sessions. Additionally, the Stanford Sleepiness Scale (SSS) will be completed both before and after each scan session and at each post-LIFUP Zoom session, in

order to control for potential fatigue effects on assessment results. Participants will also be completing a truncated version of the Phenomenology of Consciousness Questionnaire (PCQ) immediately after each scan session, and an experimental probabilistic learning task at each follow-up Zoom session.

STUDY DESIGN

The design is comprised of 2 in-person sessions, a consenting/intake Zoom session, a brief PKG setup Zoom session, 2 post-LIFUP follow-up Zoom sessions, 4 brief follow-up phone calls, and 4 weeks of round-the-clock PKG data collection. All in-person sessions will be held in private rooms on the C-level of the Semel Institute at UCLA, with scans taking place at CCN. All virtual sessions will take place over UCLAHealth HIPAA-secure Zoom. Staff will conduct all Zoom calls and phone calls from private locations to ensure participant confidentiality.

Design Overview

- Pre-screening: upon first contact by the participant, we will conduct an initial screening aimed at ensuring the participant meets inclusion criteria.
- During the intake Zoom session, we will conduct remote consenting procedures and MRI safety screening, and collect data necessary for PKG setup.
- During the remote PKG setup session, we will obtain a Zoom recording of the participant putting on the PKG device and familiarize the participant with the usage of the device.
- During in-person session #1 we will conduct consent procedures, pre-LIFUP behavioral and motor testing, MRI, either LIFUP or sham stimulation during the MRI, and post-LIFUP motor testing.

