These calls will take place seven days after each in-person session. The aim of these calls is to (a) collect information on any perceived changes since the LIFUP session or prior follow-up sessions, and (b) walk the participant through the process of syncing the PKG device in order to ensure successful data transfer, (c) collect feedback on participant experience with the study, and (d) provide instructions for returning the PKG device.

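### The Detailed Design times Post-LIFUP Remote Session 2 from the first in-person session and One-week Call 2 from each session, which contradicts the Design Overview and the stated number of calls

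*Combined protocol and SAP*

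**What the plan says.** The plan describes the follow-up schedule at three levels.

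- **Study Design, opening paragraph.** It counts "2 post-LIFUP follow-up Zoom sessions, 4 brief follow-up phone calls, and 4 weeks of round-the-clock PKG data collection".
- **Design Overview.** On remote testing: "48-72 hours after each in-person session, behavioral testing will be administered, as well as motor testing that can be conducted remotely". On calls: "4 and 7 days after each in-person session, a brief follow-up call will be conducted".
- **Detailed Design, session by session.** In-Person Session 2: "This session will take place two weeks after the first in-person session". Post-LIFUP Remote Session 1 and Post-LIFUP Remote Session 2 both carry the sentence "This session will take place 48-72 hours after the first in-person session". Four-day calls: "These calls will take place four days after each in-person session". One-week Call 1 is tied to the first in-person session only. One-week Call 2: "These calls will take place seven days after each in-person session". Its content includes syncing the PKG, collecting feedback on the study and explaining how to send the device back.

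PKG wear is described in Motor Assessment, in the Design Overview and under the Remote PKG Setup Session. All three run it from a week before the first in-person session to a week after the second.

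**The concern.** The study is a two-period crossover: each participant has active sonication at one visit and sham at the other. A within-person comparison at a given time point needs a measurement at that time point after both visits. If Remote Session 2 is held when its own entry says, both Zoom sessions follow visit 1 and neither follows visit 2.

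The measures at risk at 48 to 72 hours are the learning task, UPDRS parts 1, 2 and 4, part 1 of the TETRAS, STAI-State, BDI, RBDSQ and the Zoom administration of the SSS. The learning task is the most exposed. The Design Overview names it as a dependent variable, it is given only at the follow-up Zoom sessions, and it has no baseline. On the literal schedule each participant would do it twice under one condition and never under the other.

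The Detailed Design is the section that staff would schedule from, and all later sessions are booked at the intake Zoom session. A wrong anchor could therefore pass straight into the calendar, and a missed 48-to-72-hour window cannot be recovered. The Call 2 entry would also have staff explain device return halfway through the wear period.

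**Working it through.** **Inputs.** Session 1 is day 0. Session 2 is two weeks later, day 14 (Detailed Design, In-Person Session 2). The other offsets are those set out above.

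**The plan's own figures.**
- PKG wear: from day 0 - 7 = -7 to day 14 + 7 = 21, so 28 days or 4 weeks. This reproduces the stated duration.
- Calls under the Design Overview: days 0 + 4, 0 + 7, 14 + 4 and 14 + 7, which are days 4, 7, 18 and 21. That is four calls, which reproduces the "4 brief follow-up phone calls" of the opening paragraph.

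**The Detailed Design read literally, against the Design Overview.**

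| Contact | Detailed Design, literal | Design Overview |
|---|---|---|
| Remote Session 1 | days 2-3 | days 2-3 |
| Remote Session 2 | days 2-3 | days 16-17 |
| Four-day calls | days 4, 18 | days 4, 18 |
| One-week Call 1 | day 7 | day 7 |
| One-week Call 2 | days 7, 21 | day 21 |
| Total calls | 2 + 1 + 2 = 5 | 4 |

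- Remote Session 2 would come 14 - 3 = 11 to 14 - 2 = 12 days before the session it is meant to follow.
- Two calls would fall on day 7, and the total of five does not match the stated four.
- The PKG return instruction would be given on day 7, which is 21 - 7 = 14 days before wear ends, and again on day 21.

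**What would still be collected after session 2 on the literal reading.**
- The post-stimulation scans.
- The same-day motor battery (UPDRS part 3, TETRAS part 2, grip strength, pegboard).
- The same-day SSS and PCQ.
- The perceived-change calls on days 18 and 21.
- PKG recording to day 21, provided the device has not been sent back.

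What would be missing is the 48-to-72-hour Zoom assessment.

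**With both contacts timed from the second in-person session.** Zoom sessions fall on days 2-3 and 16-17. Calls fall on days 4, 7, 18 and 21, a total of four. The return instruction falls on day 21 only. Every count then agrees with the opening paragraph and the Design Overview.

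**The case against.** The strongest reply is that nobody would run the study this way. The Design Overview says plainly that remote testing follows each session. The four-day calls, made after both visits, ask about changes since the Zoom session, which presupposes one Zoom session per visit. Remote Session 2 is numbered 2 and sits directly after In-Person Session 2. The literal reading would have two one-hour sessions with the same content in one 24-hour window. Call 2 has a singular heading over a plural sentence that closely matches the four-day entry. All of this points to copied text, and that part of the reply stands.

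It also disposes of four stronger readings that a reader might infer.

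- **That the plan intends to omit follow-up after session 2.** The Design Overview says the opposite. This is a contradiction between sections.
- **That no remote outcomes follow session 2.** The calls on days 18 and 21 and the PKG recording do follow it. Only the Zoom assessments are at issue.
- **That precision falls by a fixed multiple.** With 30 participants split evenly by order, an unadjusted comparison of 15 with 15 has variance 2s²/15, against 2s²(1 - ρ)/30 for 30 pairs. The ratio is 2/(1 - ρ), or 4 at ρ = 0.5 and 6.7 at ρ = 0.7. Those correlations are assumed, since the documents give none, and the formula suits only an outcome without a baseline, such as the learning task. Where a pre-stimulation value exists, baseline adjustment under the same ρ changes the ratio to 2(1 + ρ), or 3.0 and 3.4. The documents also set out no specific analysis of the 48-to-72-hour outcomes. No single multiple can serve as a general magnitude.
- **That half the PKG data would be lost.** An instruction on how to return the device is not its return. Wear through the week after session 2 is stated in three places, and the literal Call 2 on day 21 still includes a sync. Loss depends on participants acting on the day-7 instruction.

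One further qualification applies. Motor Assessment says the whole motor set is repeated after each scan, while the Detailed Design lists only UPDRS part 3 and TETRAS part 2 from those two scales. On the broader reading, the other parts would have a same-day value after session 2, but still none at 48 to 72 hours. The learning task is unaffected by this point.

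The objection does not remove the inconsistency. The operative section still carries two timings that cannot both be followed with the rest of the plan.

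**Conclusion.** Wrong as written. The Remote Session 2 timing contradicts the Design Overview. The Call 2 timing contradicts the number of calls and puts a PKG return instruction in the middle of the wear period. Both follow from the text alone and need no statistical assumption beyond the two-week gap between sessions.

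The consequence is conditional on staff following the Detailed Design to the letter. In that case no participant would have a 48-to-72-hour Zoom assessment after session 2, and the within-person active-versus-sham comparison at that time point would be lost, most seriously for the learning task. The imaging aims and the same-day motor comparison would stand. This is a schedule inconsistency to correct, and it is not a flaw in the crossover design.

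**What to change.** In the Detailed Design, time Post-LIFUP Remote Session 2 at 48 to 72 hours after the second in-person session. Time One-week Call 2, with its feedback and device-return items, at seven days after the second in-person session only. Check both entries against the opening Study Design paragraph and the Design Overview, and check that any scheduling template used at intake carries the same anchors. These are assessment and contact timings and do not touch treatment.

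The cost is two wording corrections, with no added visits, staff or participants. If any participant has already been scheduled, confirm from the visit records when Remote Session 2 and the return instruction actually took place, and report any departures.
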